2.3.3 Clinical study of an ophthalmic solution of naphazoline 0.1% and hypromellose 0.5%

An open-label, single-center, observational, prospective clinical study included thirty healthy volunteers. Volunteers were administered a 0.1% naphazoline and 0.5% hypromellose solution four times daily for ten days. Results showed no changes in conjunctival hyperemia, conjunctival discharge, ciliary injection, chemosis, and rose bengal and fluorescein staining. However, 86% of patients experienced burning, 70% of which was mild and the remainder moderate; 6.6% had mild red eyes; and 6.6% had mild ocular pain. The mean burning score was 0.6861, with a standard deviation of 0.42 and a standard error of 0.016. Student's t-test showed a $p > 0.05$, leading to the conclusion that the burning score was not statistically significant. The study concludes that the solution of naphazoline 0.1% and hypromellose 0.5% is safe for application to the ocular surface of healthy volunteers. [28]

2.4 Background on the research

2.4.1 About the research question

Is the application of PRO-185 ophthalmic solution safe and tolerable in clinically healthy subjects?

The importance of the question preceding this paragraph is that there are no clinical studies with products identical to the PRO-185 solution, although there are studies with similar products (different concentration and excipients).

2.5 Risk-benefit evaluation

2.5.1 Known potential risks

Formulations containing naphazoline and/or hypromellose at the same concentrations as PRO-185 are available over-the-counter without the need for clinical or preclinical studies in high surveillance countries.[11] The risks associated with the use of this product in specific populations are described below; however, the use of this medication in the study will be in a population group without the alterations or characteristics described below.

Patients with high blood pressure, cardiovascular abnormalities, hyperglycemia, hyperthyroidism, infections, and corneal wounds should use products containing naphazoline with caution due to the risk of aggravation of these conditions.[29]

Patients with angle-closure glaucoma or closed angles may experience significant increases in intraocular pressure and should not use products similar to PRO-185.[29] [30] [31]

Overuse of this product may cause rebound conjunctival hyperemia.[29] [11]

Some patients, when using this product as recommended, may experience pharmacological mydriasis, with the resulting decreased vision.[11]

Ophthalmic vasoconstrictors, such as this product, should not be used in children under 12 years of age, and serious reactions requiring hospitalization have been reported with accidental ingestion of naphazoline products by children.[29] [32]

Administration of this product during pregnancy and lactation is prohibited.[29] [32]

Although menthol is present as one of the components, it is an excipient and is present at a concentration 80 times lower than the concentration that demonstrated mild irritation in repeated-dose irritability tests, and 10 times lower than the lowest concentration that demonstrated no irritating effects. Therefore, no additional safety data are expected from incorporating it as an excipient in the PRO-185 formulation. Furthermore, there is already experience in other markets with the use of eye drops with menthol as an excipient, and a lubricant and vasoconstrictor.[25]

2.5.2 Known potential benefits

The benefit of the drug in the target population is a reduction in hyperemia or ocular redness. [11] [12] [13] However, as this is a Phase I study, the study population will be a healthy population. Therefore, no direct benefit is expected for each individual, and the benefit of the research will be to understand the formulation's behavior and to have more data on its safety in order to prevent or identify adverse effects in users or problems with tolerance.

2.6 Problem statement

There are many formulations on the market containing naphazoline or hypromellose, some of them a combination of both. However, although there is experience with these products in the post-marketing stages, there are no published clinical studies that have examined the behavior of these drugs.

Since these products can be approved for marketing directly, without the need for clinical trials, there is little information available in the medical literature on these products. Furthermore, when they are marketed as over-the-counter products, the information included in the instructions or prescribing information is summarized and, in most cases, lacks a description of the experience of the drug's post-marketing behavior.

2.7 Justification of the study

Laboratorios Sophia, SA de CV, has conducted a preclinical and phase I clinical study of a similar formulation, but with a higher concentration of components. The reduction in the concentration of the main components (naphazoline and hypromellose) in the PRO-185 solution compared to this formulation studied could mean greater safety of PRO-185, but not necessarily greater tolerance, since the excipients may be involved in clinical manifestations unrelated to the main components.

Menthol has been used in ophthalmic preparations to relieve visual fatigue and ocular discomfort. [23] The inclusion of menthol among the excipients in PRO-185, as well as the lack of clinical evaluation of this formulation, necessitates clinical evaluation of the product. This would provide a more complete safety and tolerability profile.

In a preclinical safety and toxicity study of PRO-185 ophthalmic solution in New Zealand albino rabbits, the drug was shown to be non-toxic and safe to administer. Information also indicates that, at the menthol concentration used in Draize tests, there were no irritating or toxic effects.

Because there is preclinical evidence of safety and toxicity with the PRO-185 formulation, as well as the absence of irritation at the concentration used; and because there are ophthalmic products with menthol as an excipient in similar combinations on other markets, it was decided to advance to clinical research to test the safety and tolerability of PRO-185 in a controlled environment with healthy subjects.

3. Objectives and hypotheses

3.1 Objectives

3.1.1 Main objective:

- To evaluate the safety and tolerability of PRO-185 ophthalmic solution in ophthalmologically healthy subjects.

3.1.2 Specific objectives:

- To evaluate the safety of PRO-185 ophthalmic solution by measuring the incidence of subjects who present an increase of > 5 mmHg in intraocular pressure after 20 minutes of application compared to the initial value.
- To evaluate the safety of PRO-185 ophthalmic solution by measuring the incidence of subjects experiencing a heart rate variation of >15 beats per minute 20 minutes after application.
- To evaluate the safety of PRO-185 ophthalmic solution by measuring the incidence of subjects with an increase in systolic blood pressure of >15 mmHg or >10 mmHg in diastolic blood pressure 20 minutes after application.
- To assess tolerability by the incidence of grade 3 and 4 conjunctival hyperemia.
- To assess tolerability by the incidence of pharmacological mydriasis.
- Evaluate tolerability by the incidence of expected and unexpected adverse events.

3.2 Hypothesis

H_0 = PRO-185 ophthalmic solution is safe and tolerable for ophthalmic use, as it occurred in 20% or less of subjects with any of the following adverse events: increased intraocular pressure (IOP >5 mmHg), heart rate variation (>15 bpm), increased systemic blood pressure [>15 mmHg systolic (SBP) or >10 mmHg diastolic (DBP)], pharmacological mydriasis, or grade 3 and 4 conjunctival hyperemia.

$$H_0: p - p_0 \leq \delta$$

H_1 = PRO-185 ophthalmic solution is not safe or tolerable for ophthalmic application because more than 20% of subjects experienced any of the following adverse events: increased IOP (>5 mmHg), heart rate variation (>15 bpm), increased systemic blood pressure [>15 mmHg systolic (SBP) or >10 mmHg diastolic (DBP)], pharmacological mydriasis, or grade 3 and 4 conjunctival hyperemia.

$$H_1: p - p_0 > \delta$$

Comparisons will be made between pre- and post-treatment measurements from visits 1 and 2, and between measurements from the baseline visit (before PT application) and measurements from the

final visit. Only one of the adverse event values described in the hypothesis need be abnormal with a frequency >20% between the comparisons (pre-treatment with post-treatment; or pre-PT baseline with values from the final visit) for the null hypothesis to be rejected.

4. Study design

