7.5.10 Delivery of material for the subject

This refers to the provision of the subject's ID card and the subject's diary. The ID card will serve as identification with the treatment assignment number; this card can also serve as an appointment card. The Subject's Diary is used to record the number of times the treatment is administered.

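### The safe-and-tolerable verdict is decided on five measured signs, so burning, stinging and the other expected symptoms cannot affect it, although tolerance is the question that section 2.7 leaves open

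*Protocol*

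**What the plan says.** **The verdict.** Protocol 3.2 makes the null hypothesis "PRO-185 ophthalmic solution is safe and tolerable for ophthalmic use, as it occurred in 20% or less of subjects" with any of the listed events. The list is an intraocular pressure rise above 5 mmHg, a heart rate change above 15 bpm, a systolic rise above 15 or diastolic rise above 10 mmHg, and finally "pharmacological mydriasis, or grade 3 and 4 conjunctival hyperemia". The rejection rule refers to that list alone: "Only one of the adverse event values described in the hypothesis need be abnormal with a frequency >20% between the comparisons". The synopsis (1.1), protocol 10.1.2 and SAP 3.2 and 4.2 repeat the same five signs. SAP 3.2 gives the limit as 10% and reverses H0 and H1 in words.

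**The reason for the trial.** Section 2.7 says the lower concentrations could mean greater safety, "but not necessarily greater tolerance, since the excipients may be involved in clinical manifestations unrelated to the main components".

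**Where symptoms appear.** Protocol 3.1.2 has the specific objective "Evaluate tolerability by the incidence of expected and unexpected adverse events", and 7.4.2 makes adverse event incidence a secondary outcome. Section 7.4.5.9 names burning, stinging, irritation and tearing among the events that may occur with PRO-185. Table iii assigns adverse event incidence a binomial chi-square and gives no reference rate.

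**The earlier study.** Section 2.3.3 describes it: "An open-label, single-center, observational, prospective clinical study included thirty healthy volunteers". They received naphazoline 0.1% with hypromellose 0.5%. It found no change in conjunctival hyperemia, while "86% of patients experienced burning, 70% of which was mild and the remainder moderate".

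**The concern.** The verdict uses the word tolerable, but nothing a subject feels enters the rule. Section 2.7 gives the excipients as the reason why lower strength does not guarantee tolerance. The effects one would look for are the burning, stinging, irritation and tearing that the protocol itself expects. They have an objective and a secondary outcome, but no reference rate and no part in H0/H1.

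The final report could therefore accept H0 and call the product tolerable beside an adverse event table that shows frequent burning, and the plan would not say which of the two governs. Hyperemia, the nearest of the five signs, would help only if it rose and fell with symptoms. The sponsor's own data suggest that it need not.

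**Working it through.** **1. The plan's own figure.** The point does not depend on the sample size, but it reproduces. Inputs from protocol 10.1.2 are p0 = 0.20, margin 0.10, critical value 1.96 and power 0.80 (z = 0.842). The protocol gives no number for the expected proportion, so I assume p = 0.10 from SAP 4.1.

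n = p(1 − p) × [(1.96 + 0.842)/(p − p0 − δ)]² = 0.09 × (2.802/0.20)² = 17.66, so 18. Then 18 × 1.2 = 21.6, so 22. With the variance term as printed in the protocol, p(1 − 0.2), the result is 15.7, so 16.

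**2. What enters the verdict.**

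| Item | In H0/H1 | Reference rate |
|---|---|---|
| Intraocular pressure, heart rate, blood pressure, mydriasis, grade 3–4 hyperemia | yes | 20% (protocol), 10% (SAP) |
| Burning, stinging, irritation, tearing | no | none |
| Total adverse event incidence | no | none |

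Two other provisions do not fill the gap. Elimination for non-tolerability (5.2.1) acts on the individual and is not counted in H0/H1. The one numerical adverse event trigger in 11.3 concerns serious events.

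**3. Is hyperemia a proxy?** In section 2.3.3, 86% of 30 is 25.8, so about 26 subjects; 26/30 = 86.7%, exact (Clopper-Pearson) 95% CI 69.3% to 96.2%. Hyperemia did not change. Mild red eye was reported in 6.6%, about 2 of 30.

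**4. How much of the burning was moderate?** The text allows two readings of the 70%.

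- As a share of those who burned: 0.86 × 0.30 = 25.8% of subjects. No whole count of the 26 gives 70% (18/26 = 69.2%, 19/26 = 73.1%).
- As a share of all subjects: 0.86 − 0.70 = 16%. In counts, 21/30 is exactly 70%, which leaves 5/30 = 16.7%.

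The range is therefore 16–17% or 26%, on either side of 20%.

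**5. How much the omission can matter.** This is an illustration, not a proposed criterion. If burning were a sixth sign under the protocol's frequency rule, the first count above 20% would be 5 of 22 (22.7%).

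| True burning rate | P(at least 5 of 22) |
|---|---|
| 10% | 0.062 |
| 20% | 0.457 |
| 30% | 0.835 |
| 50% | 0.998 |
| 86% | above 0.9999999 |

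Reading H0 instead as a test against 0.20 + 0.10 = 0.30 (exact, one-sided 0.025), rejection needs 12 of 22, and power at 86% is still above 0.9999. Under the rule as written, burning contributes nothing at any of these rates.

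**The case against.** The best defence is that symptoms are handled, only elsewhere. Adverse events are assessed at every visit, before and after application at visits 1 and 2, with targeted questioning (7.4.5.9). Section 8.3 asks for every undesirable symptom whether related or not, 8.4 defines mild, moderate and severe, and 8.5.3 has the grade recorded. Section 2.7 asks for a fuller safety and tolerability profile, and incidence by severity would supply one. All of this stands. It means the data will exist, so a reader who inferred that symptoms are ignored, or that the trial cannot address 2.7, would go too far. What it does not do is connect those data to the conclusion.

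Other stronger readings also fail.

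- **That PRO-185 will burn at 86%.** The earlier product was 0.1%/0.5%, against 0.03%/0.2% here. The protocol also puts menthol at 80 times below the mildly irritating concentration and 10 times below the lowest one tested (2.2.3).
- **That the earlier study made the same omission.** It scored burning and tested the score, and it concluded on safety.
- **That moderate burning there exceeded 20%.** This holds on only one of the two readings.
- **That any burning should be held to 20%.** The documents give no basis for this. Their literature annex (protocol 16.3) describes 0.1% naphazoline as well tolerated alongside mild to moderate burning.
- **That the diary excludes symptoms.** The text says "The Subject's Diary is used to record the number of times the treatment is administered", but the form itself is not in the documents.

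**Conclusion.** The point holds as a gap between the conclusion and the data behind it. In both protocol and SAP, the verdict of safe and tolerable depends on five signs, and the expected symptoms cannot move it at any frequency from 0% to 100%. This assumes that the five signs themselves stay within limits. The earlier study supports one inference only: hyperemia cannot be relied on to reveal symptoms, since about 26 of 30 subjects burned without a change in it. The PRO-185 rate is unknown.

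This should be fixed before the analysis. It does not invalidate the trial, because the symptoms are collected and graded, and what is missing is their place in the conclusion.

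**What to change.** 1. In protocol 3.2 (and the matching text in 1.1 and 10.1.2) and SAP 3.2, limit the H0/H1 conclusion to the five named signs.
2. Base any overall statement that PRO-185 is tolerable also on the adverse event data already collected. Report the number and percentage of subjects with any, and with moderate or severe, ocular burning, stinging or irritation, using the grades of section 8.4, each with an exact 95% CI. This replaces the binomial chi-square in protocol Table iii, which has no reference rate to test against. The adverse event row of SAP Table 2 needs the same change.
3. Do not carry the 20% limit over to any burning. With 22 subjects, a true rate equal to that limit would be flagged with probability 0.457. If the sponsor wants a symptom threshold, it must justify and prespecify one.
4. Reconcile the protocol's 20% with the SAP's 10% and its reversed wording of the hypotheses in the same amendment.

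A per-dose symptom mark in the diary is optional; it would change a subject document that needs committee approval. Otherwise the cost is wording and tabulation, with no new visit, endpoint or sample size. The downside for the sponsor is that the tolerability statement may look less favourable.

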1.3 Subject's activity schedule

Procedures	Baseline visit		Visit 1		Visit 2		Final visit
	Day 1		Day 3 (+1)		Day 8		Day 10 (+1)
	Pre-TP	Post -	Pre -	Post-	Pre -	Post-	Without
	TP		Tx	Tx	Tx	Tx	treatment
FCI Signature	X						
Medical record	X						
Eligibility criteria	X						
Subject code assignment	X						
Adverse events	X	X	X	X	X	X	X
Heart rate	X	X	X	X	X	X	X
Respiratory rate	X		X		X		X
Blood pressure	X	X	X	X	X	X	X
Temperature (°C)	X		X		X		X
Urine pregnancy test	X						X
AVMC	X		X		X		X
Anterior segment evaluation	X	X	X	X	X	X	X
Pupillary diameter measurement	X	X	X	X	X	X	X
Eye stains	X	X	X	X	X	X	X
Intraocular pressure	X	X	X	X	X	X	X
Gonioscopy	X						
Pharmacological mydriasis (phenylephrine/tropicamide)	X						
Evaluation of the posterior segment	X		X		X		X
Application of PRO-185 during a visit			X		X		
Delivery of material for the subject		X					
Delivery of the study medication		X					

Procedures	Baseline visit		Visit 1		Visit 2		Final visit
	Day 1		Day 3 (+1)		Day 8		Day 10 (+1)
	Pre-TP	Post -	Pre -	Post-	Pre -	Post-	Without
	TP	Tx	Tx	Tx	Tx	Tx	treatment
Evaluation of concomitant medications	X		X		X		X
Adherence assessment			X		X		
Return of study medication						X	
Withdrawal from the subject's diary						X	

PRE-TP: prior to application of 0.8% tropicamide and 5% phenylephrine ophthalmic solution (TP Ofteno[®]), indicates that the checks will be performed prior to pharmacological mydriasis. Post-TP: post application of the TP Ofteno[®] solution, indicates that the checks will be performed with pharmacological mydriasis. Pre- Tx : pretreatment, indicates the checks to be performed before the application of the investigational medicinal product. Post-Tx : post-treatment, indicates the evaluations to be performed within 20-40 minutes after the application of the investigational medicinal product. ICF: informed consent form. BCVA: best corrected visual acuity.

2. Introduction and background

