2.2.1 Naphazoline

Naphazoline, classified by its chemical structure as an imidazole derivative, differs from other adrenergic agonists by the replacement of the benzene ring with an unsaturated ring. In general, naphazoline has a higher affinity for the α -adrenergic receptor than for the β -adrenergic receptor. After application to the ocular surface, naphazoline induces marked vasoconstriction by stimulating α -adrenergic receptors on vascular smooth muscle. Imidazole derivatives, such as naphazoline, have the advantage over phenylephrine in that they are less likely to induce rebound congestion and mydriasis. [12] [14] [5]

In most cases of conjunctival hyperemia, naphazoline has an immediate and prolonged vasoconstrictive effect on the bulbar and eyelid capillaries of the conjunctiva. If patients have superficial corneal vessels, they may also be constricted. [14]

Naphazoline can lower intraocular pressure by agonizing α -2 adrenergic receptors, thereby decreasing aqueous humor formation. The pressure reduction effect of naphazoline depends on the dose administered and the patient's sensitivity. [15]

Systemic absorption has been reported after topical application of naphazoline solutions. Although not administered systemically, it can be absorbed through the gastrointestinal tract. The onset of naphazoline's action (conjunctival vasoconstriction) can be felt within 10 minutes and last up to 6 hours. [16]

Hurwitz and Thompson studied the effects of 0.1% naphazoline in over 100 subjects with congested and normal eyes. Slit-lamp evaluations revealed constriction of the conjunctival vessels, with no effects on the deep vessels. No accommodative effects were observed at this concentration. [5]

The incidence of serious adverse reactions is low in patients receiving naphazoline ophthalmic solution at therapeutic doses. Excessive doses and/or prolonged use may irritate the conjunctiva and cause systemic adverse effects. [17]

Ophthalmic naphazoline may cause blurred vision, mild transient itching, irritation, mydriasis, and increased or decreased intraocular pressure. Application of naphazoline to the conjunctiva may release pigment granules from the iris. Rebound congestion, characterized by reactive hyperemia, frequently occurs with prolonged use. [17]

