6.1.3 Treatment with the investigational product

The investigational product will be administered at the conclusion of the baseline visit, and the subject will administer the drops approximately every 2-4 hours between drops, applying them a total of 4 times per day to each eye.

Baseline visits, 1, and 2, should be completed in the morning, before 11 a.m., to allow the patient more time to apply PRO-185 throughout the day. During visits 1 and 2, the patient will come to the clinic without having previously applied the investigational product. The first application will be considered the drop applied by the researcher during the visit. For visit 1, the patient will be required to apply the product three times after the visit has concluded. For visit 2, the patient will not need to apply the product again because the investigational product will have been returned to the researcher.

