7.4.5.5 Conjunctival hyperemia

It is defined as the simplest reaction of the conjunctiva to a stimulus. A red appearance is observed secondary to vasodilation of the conjunctival vessels of varying intensity. It is graded using the Efron scale. [38]

Figure 1. Efron scale for conjunctival hyperemia

Management as AE: Grade 3 and 4 at visits 1, 2 and final will be considered as aggravation and adverse event.

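### The Protocol conflicts with itself on whether pre-dose hyperemia grades at visits 1 and 2 count toward the primary rule, and the comparison list in 3.2 leaves them out

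*Protocol*

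**What the plan says.** **Decision rule.** Protocol 3.2, repeated in synopsis 1.1, lists the primary comparisons. The first is "Comparisons will be made between pre- and post-treatment measurements from visits 1 and 2"; the second sets the baseline visit, before the dilating drops, against the final visit. The rule is tied to that list: "Only one of the adverse event values described in the hypothesis need be abnormal with a frequency >20% between the comparisons". Protocol 10.1.2 times the sample-size event the same way, at 20 minutes after application against the initial value, and SAP 4.2 repeats that timing.

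**Timing of the examinations.** In the Protocol schedule (1.3 and 7.6.2), Post-Tx "indicates the evaluations to be performed within 20-40 minutes after the application of the investigational medicinal product". For visits 1 and 2, section 6.1.3 says "the patient will come to the clinic without having previously applied the investigational product". The last drop is the one given in clinic on Day 8, and the final visit is Day 10 (+1).

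**Pharmacology.** Protocol 2.2.1 says the vasoconstriction "can be felt within 10 minutes and last up to 6 hours". On rebound it says "Rebound congestion, characterized by reactive hyperemia, frequently occurs with prolonged use". Section 2.5.1 links rebound to overuse, and 7.4.5.9 lists rebound hyperemia among the possible adverse events.

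**Text pointing the other way.** Protocol 3.1.2 sets the hyperemia objective as the incidence of grades 3 and 4, without a time point. Section 7.4.5.5 states: "Grade 3 and 4 at visits 1, 2 and final will be considered as aggravation and adverse event". It makes no distinction between pre-dose and post-dose grades.

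**Analysis text.** Protocol 10.3.2.1 and SAP 6.2.1 each name a test for hyperemia, but neither says which examination supplies the grade.

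**The concern.** For a redness reliever, a grade taken 20-40 minutes after the drop largely reflects the intended effect. The final visit, off drug, answers a different question. The pre-dose grades at visits 1 and 2 are where on-treatment rebound or cumulative irritation would be least suppressed. Irritation matters here because Protocol 2.7 says the excipients may affect tolerance independently of the active components. If 3.2 is followed as written, these grades enter only as the before value.

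Under 3.2 a single event type above 20% is enough to reject the hypothesis that the product is safe and tolerable. The definition of the hyperemia event can therefore decide the trial's conclusion by itself. Leaving out grades at which redness is present can move the result in one direction only, toward tolerable.

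**Working it through.** **Step 1. List the examinations.** Hyperemia has no row of its own in the schedule, so I take it to be graded at the anterior-segment evaluation. The Protocol marks that evaluation at five post-baseline points.

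| Examination | Drug state | Role under 3.2 |
|---|---|---|
| Visit 1 Pre-Tx | on treatment, no drop yet that day | reference only |
| Visit 1 Post-Tx | 20-40 min after drop | evaluated |
| Visit 2 Pre-Tx | on treatment, no drop yet that day | reference only |
| Visit 2 Post-Tx | 20-40 min after drop | evaluated |
| Final | 10 - 8 = 2 to 11 - 8 = 3 days after last drop | evaluated |

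Three of five are evaluated. Both evaluated on-treatment points lie inside the stated action window (10 minutes to 6 hours). No contrast of baseline with a Pre-Tx grade is listed.

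**Step 2. Set the definitions side by side.** Take a subject with grade 3 before the drop at visit 2, grade 1 after it and grade 1 at the final visit.
- 3.2 and 10.1.2: no evaluated value is grade 3-4, so no primary event.
- 7.4.5.5: an adverse event, which enters secondary adverse-event incidence (7.4.2).
- 3.1.2: grade 3-4 has occurred, so the subject counts toward the incidence.
- 10.3.2.1 and SAP 6.2.1: silent.

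For pupil diameter, 7.4.5.4 compares baseline with every other measurement as well as pre-dose with post-dose. The any-examination approach is thus already used for another primary variable.

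**Step 3. The plan's own sample size.** With p = 0.10 (not given as an expected value in the Protocol; taken from the 10% in SAP 4.1), p0 = 0.20, margin 0.10, z = 1.96 and power 0.80:

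n = p(1-p)[(1.96 + 0.84)/(p - p0 - margin)]^2 = 0.09 x (2.80/0.20)^2 = 17.6 (17.7 with unrounded z), rounded up to 18. Then 18 x 1.2 = 21.6, rounded up to 22.

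The factor printed in the Protocol, p(1-0.2), gives 15.7. Neither 18 nor 22 changes with the choice of examinations.

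**Step 4. Effect on the rule, by assumption.** Exceeding 20% of 22 takes 5 subjects (5/22 = 22.7%; 4/22 = 18.2%). Let q be the true share with a pre-dose grade 3-4 on treatment. Let m be the fraction of those below grade 3 at every evaluated point. Assume no other grade 3-4 events, and that a grade 3-4 still present post-dose counts (3.2 does not say so). The number observed is then Binomial(22, q(1-m)), and the table gives P(X >= 5).

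| q | m = 0 (or Pre-Tx grades count) | m = 0.25 | m = 0.5 | m = 0.75 | m = 1 |
|---|---|---|---|---|---|
| 0.1 | 0.06 | 0.02 | 0.004 | <0.001 | 0 |
| 0.2 | 0.46 | 0.23 | 0.06 | 0.004 | 0 |
| 0.3 | 0.84 | 0.57 | 0.23 | 0.02 | 0 |
| 0.4 | 0.97 | 0.84 | 0.46 | 0.06 | 0 |

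The documents supply neither q nor m. The table shows only how sensitive the rule would be.

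**The case against.** The strongest reply is that the Protocol can be read to count these grades already. Section 3.1.2 times the pressure and heart-rate objectives at 20 minutes but leaves hyperemia untimed. Grades 3 and 4 are excluded at entry (5.1.2), so any later one is new and needs no contrast. The hypothesis calls its items adverse events, and 7.4.5.5 defines that adverse event without a pre-dose or post-dose limit. This stands as a possible reading, which is why the defect is an unresolved conflict and not a settled exclusion. It does not remove the conflict, because the explicit list in 3.2 and the timing in 10.1.2 say otherwise.

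Three stronger inferences are not supported:

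- **That these grades are never counted.** Section 7.4.5.5 sends them at least to secondary adverse-event incidence, so safety reporting does not lose them.
- **That a fall from grade 3 to grade 1 is scored as an improvement.** The before-after difference in 10.3.2.1 applies to the quantitative variables. Hyperemia is ordinal with its own test, and no change score is defined for it.
- **That substantial rebound is to be expected.** The documents tie it to prolonged use or overuse, and treatment lasts 8 days. Section 2.2.1 calls imidazole derivatives less prone to rebound than phenylephrine. A 10-day healthy-volunteer study in annex 16.3 found none after stopping. The volunteer study in 2.3.3, at 0.1% naphazoline for ten days, reported no change in conjunctival hyperemia and 6.6% with mild red eyes. The off-drug final visit can also catch withdrawal redness that lasts 2-3 days.

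The last point lowers the likely frequency. It does not justify a rule that could not see the event if it occurred.

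**Conclusion.** The point holds as a conflict over the primary event. Protocol 3.2 and 10.1.2 use the visit 1 and 2 pre-dose hyperemia grades only as references. Protocol 3.1.2 and 7.4.5.5 imply that a grade 3-4 there counts. The analysis sections of both documents leave it open. On the 3.2 reading, redness or irritation that is present pre-dose, masked post-dose and resolved by the final visit escapes the primary rule, so that rule leans toward tolerable.

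The size is unknown. It could be nil if such redness does not occur in 8 days. It could be decisive if it is common and usually masked: 6/22 (27%) with complete masking would read 0/22. A reader should not take that example as a forecast, since its rate, its complete masking and its complete resolution are all assumed. The conclusion also assumes that the previous day's last drop has largely worn off by the morning visit; the documents do not fix that interval.

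This should be corrected before analysis, but it does not put safety reporting at risk.

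**What to change.** Define the primary hyperemia event once: Efron grade 3 or 4 at any post-baseline examination (visit 1 Pre-Tx and Post-Tx, visit 2 Pre-Tx and Post-Tx, final), counted once per subject. Carry that definition into Protocol 1.1, 3.2, 10.1.2 and 10.3.2.1 and into SAP 4.2 and 6.2.1, so that they agree with Protocol 3.1.2 and 7.4.5.5.

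Confirm that SAP Table 1 includes the Pre-Tx anterior-segment examination. As it reads, it marks that examination only in Post-Tx columns and not at the final visit, unlike the Protocol schedule. This may be damage to the table in conversion.

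Cost: no added visits, procedures or subjects under the Protocol schedule. The observed hyperemia rate may be slightly higher. Because a primary event definition changes, an amendment through the committees and the regulator is needed (Protocol 11.2).
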